2.2 INVESTIGATION OBJECTIVES

The primary objective of this investigation is to demonstrate the effectiveness of the SIFS in a lumbar interbody application. Effectiveness will be determined as a composite score that represents patient success. To be considered a patient success, each of the following criteria must be met at the 24-month study interval:

- Pain – Improvement in low back pain score evidenced by a 20 mm reduction on a 100 mm Visual Analog Scale (VAS) when compared to baseline (Note: a lower VAS pain score indicates less pain),
- Function – Improvement in low back function evidenced by a 15 point decrease of the Oswestry Disability Index (ODI) score compared to baseline. (Note: a higher ODI score indicates a greater disability with respect to low back function),
- Fusion – Bridging bone demonstrated on CT Scan
- Safety – Freedom from device-related Serious Adverse Events and secondary surgical interventions at the index level through the 24-month study interval.

In addition to the above stated primary objective, this investigation will yield data on the following outcomes, subject parameters and clinical utility:

- Variable scores over time (pain, function, fusion) as individual parameters
- Adverse Event rate(s) reported by relatedness and severity
- Neurological status over time
- Quantitative/qualitative radiographic data over time specific to the index level and contiguous levels (translation, angulation, disc height, and device position)
- Demographics
- Hospitalization Utility (duration of surgery, estimated blood loss and duration of hospitalization)
- Work status over time
- Pain medication use

Data collection is not limited to the above data points. Additional parameters will be reported on as appropriate. For a more detailed list of supplemental outcomes refer to Section 3.2 Scientific Soundness and Statistical Analysis.

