3.2.7 Analysis of Additional Outcomes

The additional outcomes for this study are as follows:

- Mean low back VAS pain score over time through the 24-month interval
- Mean lower extremity (right and left leg) VAS scores over time through the 24-month interval
- Mean ODI score over time through the 24-month interval
- Fusion at the 12-month and the 24-month interval
- Occurrence of device-related Serious Adverse Events through the 24-month interval
- Occurrence of study-related Adverse Events through the 24-month interval
- Neurological status assessment (strength, sensation, and reflexes) over time through the 24-month interval (reporting categorized as improved, maintained, or reduced with new or increased neurological deficit being further categorized as transient (< 3 months/90 days) or longer term \geq 3 months/90 days);

- Radiographic data observed over time specific to the index level (translation, angulation, disc height, and device position)
- Subject satisfaction with procedure/outcome
- Work status over time
- Pain medication use over time
- Operative time
- Estimated blood loss
- Duration of hospitalization
- Graft site pain (as applicable)
- Adjacent segment status at 24-months post-operative assessed by quantitative and qualitative radiographic data (translation, angulation, and disc height)

The mean low back pain score over time through the 24-month interval will be summarized using descriptive statistics and a 95% confidence interval based upon the t-distribution. The mean lower extremity (right and left leg) VAS scores over time and the mean ODI score over time will be analyzed in the same manner.

The number and percentage of subjects achieving fusion at the 12-month and 24-month intervals and the corresponding 95% exact (Clopper-Pearson) confidence intervals for the true proportion of subjects achieving fusion will be presented.

The number and percentage of subjects with any device-related serious adverse events (SAEs) and with any study-related adverse events will be presented, together with 95% exact (Clopper-Pearson) confidence intervals for the true proportions. AEs will be summarized at the subject level by type of event using frequencies and percentages. AEs will also be tabulated at the event level by severity and by relatedness.

Neurological status for strength, sensation, and reflexes will be summarized by time point using counts and percentages and 95% exact (Clopper-Pearson) confidence intervals for the true proportions.

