Radiographic data for translation, angulation, and disc height specific to the index level will be summarized by time point using descriptive statistics and a 95% confidence interval based upon the t-distribution. Device position will be summarized by time point using counts and percentages and 95% exact (Clopper-Pearson) confidence intervals for the true proportions.

Subject satisfaction with the procedure/outcome will be summarized using counts and percentages and 95% exact (Clopper-Pearson) confidence intervals for the true proportions.

Operative time, estimated blood loss, and duration of hospitalization will be summarized using descriptive statistics and a 95% confidence interval based upon the t-distribution. Work status, pain medication use, and graft site pain will be summarized by time point using frequencies and percentages and 95% exact (Clopper-Pearson) confidence intervals for the true proportions.

Radiographic data at 24-months post-operative for translation, angulation, and disc height for treated and adjacent segments will be summarized using descriptive statistics and a 95% confidence interval based upon the t-distribution.

For the analyses of these additional outcomes, there will be no imputation of missing values.

3.2.8 *Data Management Plan*

The purpose of a Data Management Plan (DMP) is to provide guidance for all aspects of data management as it pertains to this investigation. A DMP shall be in place prior to the initiation of this clinical investigation.

3.2.9 *Subject Withdrawal*

An enrolled subject is considered “withdrawn” from the investigation if their participation in the study is discontinued for any reason after signing the consent form. If a subject chooses to withdraw from the investigation, a Subject Discontinuation CRF will be completed and submitted to the sponsor as soon as it is practical. Every effort will be made to complete the trial CRFs applicable up to the point of withdrawal. If a subject voluntarily withdraws from the investigation, the data generated from their participation in the study will still be used in the overall investigation data set. Approval to use the data will be documented in the consent form.

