4.3 EXCLUSION CRITERIA

In the event a subject meets one or more of the following exclusion criteria, they shall be excluded from study participation:

- Previous implant surgery (i.e., fusion procedure or total disc replacement) at the index level (Note: Previous less invasive procedures such as laminectomy, discectomy, etc., at the index level are not considered exclusionary);
- Greater than Grade I spondylolisthesis;
- Presents with a diagnosis of symptomatic non-index level lumbar degenerative disc disease between L2 and S1. Non-index level lumbar DDD diagnosis confirmation shall be determined by subject history, physical examination, and radiographic studies with one or more of the following factors:
 - Instability as defined by >3mm translation or $\geq 5^\circ$ angulation;
 - Osteophyte formation of facet joints or vertebral endplates;
 - Decreased disc height, on average by > 2mm, but dependent upon the spinal level;
 - Scarring/thickening of the ligamentum flavum, annulus fibrosis, or facet joint capsule;
 - Herniated nucleus pulposus;
 - Facet joint degeneration/changes; and/or
 - Vacuum phenomenon;
- Active systemic infection or infection local to the surgical site;
- Active or suspected malignancy;
- Body Mass Index (BMI) of ≥ 40 ;
- Significant metabolic bone disease (e.g., osteoporosis or osteomalacia) to a degree that would contraindicate spinal instrumentation. Osteoporosis is defined as a T-score of < -2.5 on a DEXA scan. A screening questionnaire for osteoporosis, SCORE (Simple Calculated Osteoporosis Risk Estimate), will be administered to identify those patients that require a DEXA scan (a score greater than or equal to 6 requires DEXA scan);
- Taking medications that are known to potentially interfere with bone or soft tissues healing (e.g., chronic systemic steroids);
- Has a current diagnosis of substance related disorder, as defined per the Diagnostic and Statistical Manual of Mental Disorders 5th Edition, May 2013 (DSM – V);
- Has a diagnosis of somatoform, dissociative, eating or psychotic disorder per DSM – V;
- Waddell Signs of inorganic behavior (3 or more signs);

- Is a current tobacco user (current use defined as tobacco use \leq 30 days prior to surgery);
- Is a prisoner at the time of enrollment;
- If female: pregnant/contemplating pregnancy during the follow-up period;
- Enrolled in a concurrent clinical investigation that may confound the findings of the present investigation.

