6.0 RADIOGRAPHIC EVALUATIONS

Radiographic evaluations (x-rays) are to be performed in accordance with the study protocol. All x-rays are to be performed weightbearing (standing). Anterior/Posterior (AP) and Neutral Lateral (NL) X-rays are taken preoperatively and are repeated prior-to-discharge from the hospital and at the 6-week, 3-, 6-, 12-, and 24-month post-operative visits. The prior-to-discharge weight-bearing AP and neutral lateral X-ray will serve as the baseline postoperative assessment of disc space height. Lateral Flexion/Extension X-rays are taken preoperatively and repeated at the 6-, 12- and 24-month post-operative visits to document the preoperative condition of the involved disc space and to evaluate stability and fusion of the operative level during follow-up. X-rays shall be obtained with a study-specific magnification marker in place. The marker allows the core lab to adjust for magnification discrepancies and ensure measurement accuracy. ***Further, to help assure accurate reporting of quantitative sagittal alignment by lumbar segment in this investigation, neutral lateral radiographs shall adequately display the vertebral bodies from T-12 through S1.***

A CT scan will be performed at the 12-month study interval. In the event a subject is determined “not fused” at the 12-month timepoint per the CT scan assessment, a second CT scan would be performed at the 24-month post-op interval. **Table 2** below indicates the per protocol radiographic schedule.

Table 2: Radiographic Assessment Schedule

	Pre operative	Post operative	6 week	3 month	6 month	12 month	24 month
MRI (T2 weighted image) [†]	X						
Standing AP X-rays	X	X	X	X	X	X	X
Standing NL X-rays	X	X	X	X	X	X	X
Lateral flexion-extension films	X				X	X	X
CT Scan						X	X*

[†]Or other appropriate radiologic study as defined per protocol.

*Performed only if determined to be not fused per CT scan at the 12-month interval

The following radiographic analyses are planned:

Radiographic assessment for bridging bone will be completed by two board-certified radiologists. A third radiologist will provide a “tie-breaker” reading if needed. Radiologist evaluations will be centralized for films from all investigational sites.

Fine-cut CT images with sagittal and coronal reconstructions will be used as the primary determinant of fusion status. X-ray images will also be subjected to a qualitative assessment to evaluate for the presence of bridging bone.

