Follow-up x-rays will be evaluated by an independent radiographic core laboratory. For this trial, the core lab will measure relative angulation and translation of the vertebral bodies at the involved motion segment during flexion/extension motion, and will also measure both anterior and posterior disc space height. The core lab will further evaluate for device condition/configuration and position changes over time.

Imaging will be reviewed by the radiologist/core lab for the presence of any of the following negative conditions:

- Expulsion: Implant moved outside of disc space
- Migration: > 5 mm migration of implant from original position
- Subsidence: > 5 mm loss of disc height
- Significant Radiolucency: > 50% of implant/endplate interface shows true lucency (true lucency is black, not gray)
- Adjacent level disc degeneration, defined as:
 - > 5mm loss of disc height
 - > 3mm translation on flexion/extension
- Loosening and/or breakage of pedicle screws

The radiographic assessment protocol, film labeling instructions, and other radiographic reference material are included in **Appendix IV**.

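### Adjacent segments are summarised only as 24-month values, so change after fusion cannot be separated from what was there before surgery, and the translation criterion has no stated pre-operative reference.

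*Combined protocol and SAP*

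**What the plan says.** Section 2.2 lists, among the data the trial will yield, "Quantitative/qualitative radiographic data over time specific to the index level and contiguous levels". Section 3.2.10 explains the absence of a control group by saying that each subject in effect serves as his or her own control over time.

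Sections 3.2.2 and 3.2.7 then list the adjacent-level outcome as "Adjacent segment status at 24-months post-operative assessed by quantitative and qualitative radiographic data (translation, angulation, and disc height"). The matching analysis in 3.2.7 is "Radiographic data at 24-months post-operative for translation, angulation, and disc height for treated and adjacent segments will be summarized using descriptive statistics", with a t-based 95% interval. The index level is treated differently in the same section: "Radiographic data for translation, angulation, and disc height specific to the index level will be summarized by time point".

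Section 6.0 has the images reviewed for the presence of several negative conditions. One is adjacent level disc degeneration, with two sub-items: a loss of disc height above 5 mm, and "> 3mm translation on flexion/extension". The text does not say whether one or both are needed.

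Section 4.3 excludes a subject who "Presents with a diagnosis of symptomatic non-index level lumbar degenerative disc disease between L2 and S1". Translation above 3 mm is one of the radiographic signs listed there.

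On the films themselves, section 6.0 says "Lateral Flexion/Extension X-rays are taken preoperatively and repeated at the 6-, 12- and 24-month post-operative visits". It ties the pre-operative flexion/extension films to the involved disc space, and the core lab's angulation and translation measurements to the involved motion segment.

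**The concern.** Some subjects with single-level disease will have changes at neighbouring levels before the operation. The clinical question about adjacent segments after a fusion is whether they changed. With no control arm, the subject's own pre-operative film is the only reference inside the trial, and the analysis section does not use it for these levels. A mean adjacent translation or disc height at 24 months says where the levels ended, but not where they started.

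The translation criterion in section 6.0 raises a second problem. A subject whose adjacent level already moves more than 3 mm without symptoms is not excluded by section 4.3. If nothing changes after surgery, that level still exceeds 3 mm on the follow-up film. Any tally of the criterion would then mix old and new findings. At stake is the interpretation of a safety-relevant descriptive result in a regulatory submission, not the primary conclusion.

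**Working it through.** **Figures in the plan.** The plan states no adjacent-segment figure, so there is none to reproduce. Its only computed figure, 87 evaluable subjects for the primary endpoint (section 3.2.4), reproduces: rejecting at 56 or more successes gives an exact one-sided alpha of 0.0487 and power of 0.801. Nothing below alters it.

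**Step 1: objective against analysis.**
- Section 2.2: index and contiguous levels, over time.
- Section 3.2.7, index level: by time point.
- Section 3.2.7, adjacent levels: 24 months only, no baseline, no change.

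The contiguous-level part of 2.2 is therefore not carried into the analysis.

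**Step 2: what the 24-month mean can show.** For each measurement, the 24-month mean equals the pre-operative mean plus the mean change. The plan reports only the left-hand side for adjacent levels, so the change cannot be recovered. Its confidence interval also needs paired values, because the variance of a difference depends on the within-subject correlation.

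**Step 3: can pre-existing translation meet the criterion?**
- Entry (section 4.3): only symptomatic non-index disease excludes, so asymptomatic translation above 3 mm at an adjacent level is eligible.
- Follow-up (section 6.0): the same 3 mm threshold is read for presence, with no condition that the finding be new.
- The disc-height item is worded as a loss, so it is already a change, although no reference film is named for adjacent levels. The gap concerns translation only.

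So it can, provided translation alone is sufficient and Appendix IV sets no reference.

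**Step 4: illustration on assumed rates.** None of these rates is in the documents. Let q be the share of subjects with persistent asymptomatic adjacent translation above 3 mm before surgery, and i the share of the rest who develop it. Assume translation alone meets the criterion. Then

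observed rate = q + (1 − q) × i, and new part = (1 − q) × i.

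| q | i | Observed rate | New part | Pre-existing share of findings |
|---|---|---|---|---|
| 0% | 5% | 5.0% | 5.0% | 0% |
| 5% | 5% | 0.05 + 0.95 × 0.05 = 9.75% | 4.75% | 51% |
| 5% | 10% | 0.05 + 0.95 × 0.10 = 14.5% | 9.5% | 34% |
| 10% | 5% | 0.10 + 0.90 × 0.05 = 14.5% | 4.5% | 69% |
| 20% | 5% | 0.20 + 0.80 × 0.05 = 24.0% | 4.0% | 83% |
| 30% | 5% | 0.30 + 0.70 × 0.05 = 33.5% | 3.5% | 90% |

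The third and fourth rows matter most. The same observed 14.5% arises from a new part of 9.5% or of 4.5%, and a 24-month reading alone cannot tell them apart. When q is zero, the absolute and baseline-referenced readings agree.

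**The case against.** The case on the other side is substantial.

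- **The listed outcome is status at 24 months, and the planned summary delivers it.** This stands. A reader might infer that the stated outcome goes unanswered, or that no longitudinal adjacent-level data are planned anywhere. Neither follows: 3.2.2 and 3.2.7 agree with each other, and 2.2 does promise data over time. The defect is that the analysis does not carry 2.2 through.
- **No rate is planned for the section 6.0 criterion.** This stands. Section 3.2.7 specifies continuous summaries for adjacent levels and no proportion with degeneration. A reader might infer that a reported rate is biased upward, but the plan defines no such rate. The problem arises only where the criterion is tallied.
- **The two sub-items may both be required.** This stands as an ambiguity. Section 4.3 says one or more factors suffice, whereas section 6.0 is silent. If both are required, stable old translation alone would not qualify and the formula above would not apply.
- **Appendix IV may name a reference film.** It holds the radiographic assessment protocol and was not available, so the text supports saying that pre-existing translation can be counted, not that it is. Such a reference would not repair 3.2.2 and 3.2.7.
- **The stakes are low.** This is one of 16 descriptive additional outcomes. That limits the priority but does not remove the mismatch.

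**Conclusion.** The point holds in limited form. Section 3.2.7 does not carry through the contiguous-level part of section 2.2, and its 24-month-only summary cannot separate adjacent-level change after fusion from the state before surgery. That conclusion rests on the text alone.

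The second part is conditional. Asymptomatic pre-existing translation above 3 mm can be counted as a follow-up finding if translation alone meets the section 6.0 criterion and Appendix IV sets no pre-operative reference. It does not extend to pre-existing disc narrowing, which the height-loss item does not count, or to symptomatic adjacent disease, which is excluded.

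The size cannot be derived from the documents. The table shows how the mixing works under assumed rates and full persistence, and is not an estimate for this trial. The primary composite, the hypothesis test and the sample size of 87 (102 with allowance for loss) are unaffected.

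**What to change.** **Sections 3.2.2 and 3.2.7.** Report adjacent-level translation, angulation and disc height pre-operatively and at 24 months, with the within-subject change and its t-based 95% interval. This brings the analysis into line with 2.2 and 3.2.10.

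**Section 6.0.**
- Name the reference film for adjacent-level disc-height loss, consistent with the use of the prior-to-discharge film as the post-operative baseline for disc height.
- State whether the two sub-items are joined by and or by or.
- Wherever the criterion is tallied, report translation above 3 mm as pre-existing or new, with the continuous change alongside. The continuous change is needed because a split at 3 mm would call a move from 2.9 to 3.1 mm new and would miss worsening in a level already above 3 mm.
- Check that Appendix IV says the same.

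**Cost.** The pre-operative and 24-month films are already scheduled, so no imaging is added. The same core lab would have to measure adjacent levels on films whose stated purpose is the involved level, which is real extra reading work. Adding 6-month translation first requires reconciling section 5.3.7, which lists only AP and neutral lateral films at that visit, with Table 1 and section 6.0, which include flexion/extension films.

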3.2.3 Statistical Methods

The statistical analysis of the data obtained from this study will be performed using SAS® version 9.1 or higher. All statistical tests will be performed at the 0.05 significance level, unless otherwise indicated.

Data collected in this study will be documented using summary tables and subject data listings. Continuous variables will be summarized using descriptive statistics, specifically the mean, median, standard deviation, minimum, and maximum, and a 95% confidence interval for the mean based

on the t-distribution. Categorical variables will be summarized using frequencies and percentages and 95% exact (Clopper-Pearson) confidence intervals for the true proportions.

All analyses of effectiveness and safety will be based upon the Treated Population defined to be all treated subjects.

3.2.4 *Determination of Sample Size*

The required sample size was calculated based on the following specifications:

1. Endpoint: success rate
2. One-sided exact binomial test for a binomial proportion
3. Alpha = 0.05
4. True percentage of successes = 68%
5. Performance Goal (null percentage of successes) = 55%
6. Power = 80%

The required sample size based upon these specifications is 87 subjects. The sample size was increased to 102 subjects to take into account an assumed 15% lost to follow-up rate.

3.2.5 *Sample Size Re-Estimation*

A sample size re-estimation will be performed based on 12-month interim data.

3.2.6 *Analysis of Primary Endpoint*

The primary endpoint for this investigation is a composite endpoint of pain, function, fusion, and safety that meets all of the following criteria at the 24-month study interval:

- Pain – Improvement in low back pain score evidenced by a 20 mm reduction on a 100 mm Visual Analog Scale (VAS) when compared to baseline (Note: a lower VAS pain score indicates less pain),
- Function – Improvement in low back function evidenced by a 15 point decrease of the Oswestry Disability Index (ODI) score compared to baseline. (Note: a higher ODI score indicates greater disability with respect to low back function),
- Fusion – Bridging bone demonstrated on CT Scan
- Safety – Freedom from investigational device-related Serious Adverse Events at the index level through the 24-month study interval.

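### The 24-month VAS and ODI means rest on attendees only, with no mean change from baseline, so outcome-related dropout would bias them; a repeated-measures model is a cheap improvement.

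*Combined protocol and SAP*

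**What the plan says.** - **Summary of pain and function.** Section 3.2.7: "The mean low back pain score over time through the 24-month interval will be summarized using descriptive statistics", with a 95% interval from the t-distribution. Leg VAS and ODI are handled the same way.
- **Missing values.** Section 3.2.7 closes with: "For the analyses of these additional outcomes, there will be no imputation of missing values".
- **Expected loss.** Section 3.2.4: "The sample size was increased to 102 subjects to take into account an assumed 15% lost to follow-up rate".
- **Data collected.** The Patient Survey carries VAS and ODI. Section 5.3.2 and Table 1 schedule it at baseline, 6 weeks and 3, 6, 12 and 24 months, with remote surveys after that.
- **Population and role.** Section 3.2.3 bases every effectiveness analysis on all treated subjects. Section 3.2.2 describes the additional outcomes as descriptive; no hypothesis is attached to them.
- **Primary endpoint, for contrast.** Section 3.2.6 fills missing 24-month composite data by last observation carried forward and then multiple imputation, using earlier post-baseline visits.
- **Control.** Section 3.2.10 explains the absence of a control group by treating each subject as his or her own control over time.

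**The concern.** Without imputation or a longitudinal model, the 24-month mean is the mean of those who provide a 24-month score. The baseline mean describes nearly everyone treated. A reader who compares the two points on the curve sees improvement mixed with a change in who is measured. The own-control argument in section 3.2.10 calls for within-subject change as the natural summary, yet mean change in VAS or ODI is not listed.

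If subjects with poor results are lost more often, the 24-month means look better than they would with everyone followed, and the intervals are centred in the wrong place. A single-arm trial has no comparison group in which a similar selection might cancel. The results are meant to support a regulatory submission (section 3.1), where mean pain and function over time will be read closely even though nothing is tested on them. For most lost subjects, baseline and some of the four earlier post-operative visits should already be on file and could inform the estimate.

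**Working it through.** **1. The plan's own figures.** Inputs from section 3.2.4: one-sided exact binomial test, alpha 0.05, goal 55%, true rate 68%, power 80%. With n = 87 and success declared at 56 or more, the exact alpha is 0.0487 and the power 0.801, so the stated 87 is reproduced. For the loss allowance, 102 × 0.85 = 86.7, or about 87 expected at 24 months. (87 / 0.85 = 102.35, so strict rounding up gives 103; the difference is immaterial here.)

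**2. Bias of the observed-case mean.** Let d be the fraction lost and G the gap in true 24-month mean between lost and retained subjects. The mean over everyone is (1 − d) × retained mean + d × lost mean, so the retained mean is off by d × G. With d = 0.15 (section 3.2.4, a planning allowance) and G assumed:

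- G = 0: no bias
- G = 10 mm: 0.15 × 10 = 1.5 mm
- G = 15 mm: 2.25 mm
- G = 20 mm: 3.0 mm

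**3. Coverage of the nominal 95% interval.** The documents give no SD; 25 and 30 mm are assumed. SE = SD / √87, which is 2.68 mm and 3.22 mm. Coverage = Φ(1.96 − b/SE) − Φ(−1.96 − b/SE), with b the bias.

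| SD (mm) | b (mm) | b/SE | Coverage |
|---|---|---|---|
| 25 | 1.5 | 0.56 | 91% |
| 25 | 2.25 | 0.84 | 87% |
| 25 | 3.0 | 1.12 | 80% |
| 30 | 1.5 | 0.47 | 92.5% |
| 30 | 2.25 | 0.70 | 89% |
| 30 | 3.0 | 0.93 | 85% |

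The range is about 93% down to 80%. The interval half-width is about 5.3 mm (SD 25) or 6.4 mm (SD 30), so the bias stays inside it.

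**4. Can earlier visits help?** A simulation used 4,000 runs per setting, n = 102 and 15% missing at 24 months. SD was 20 or 25 points and the 12- to 24-month correlation 0.5 or 0.7. Dropout depended on the 12-month score (logistic slope 0 to 1.5 per SD). All of these except n and the 15% are assumptions.

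- Attendees only, slope 0.5 to 1.5: bias −0.7 to −3.1 points, coverage 94% down to 79%.
- Estimator that also uses the 12-month score of all subjects, same settings: bias within about 0.05 points, coverage 94.5% to 95.8%.
- Slope 0: both nearly unbiased, with about 95% coverage.

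**5. Limit of that result.** The simulation satisfies missing at random by construction. If dropout depends on the 24-month score itself, borrowing the 12-month score removes roughly the squared correlation of the bias (equal SDs, approximation): 0.5² = 25% to 0.7² = 49%. Earlier visits then reduce the bias but do not remove it.

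**The case against.** The strongest reply is that no decision rests on these tables. They are descriptive, the only stated test is on the composite, and that endpoint has its own imputation plan. Saying openly that nothing is imputed is conventional and contradicts no other section. The SD, the gap and the direction of dropout are assumed, and 15% is an allowance, not an observed loss. Even on these inputs the bias is at most 3.0 / 20 = 15% of the 20 mm success threshold. The plan also limits loss at source: section 3.2.9 calls for multiple contact efforts before a subject is declared lost, and section 12.0 makes a missed 24-month examination a major deviation. All of this stands, and it makes the point an improvement, not an error.

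Some stronger readings are tempting, and the documents do not support them:

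- *Lost subjects' data are thrown away.* They are not. Their scores count at each visit they attended, and section 3.2.9 keeps the data of subjects who withdraw voluntarily. The scores merely do not inform the 24-month mean.
- *Within-subject change is ignored.* It enters the tested composite through the 20 mm and 15-point criteria. What is absent is mean change.
- *The intervals are too narrow.* Under outcome-related dropout the problem is mainly that they are mis-centred.
- *A mixed model would cure the bias.* It does so only under missing at random, which cannot be verified from the data.

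**Conclusion.** The point holds as a low-severity improvement. With the plan's own 15% allowance, the 24-month VAS and ODI means describe about 87 of 102 treated subjects, and mean change from baseline is not planned. If lost subjects would have scored 10 to 20 mm worse, the low back VAS mean looks 1.5 to 3.0 mm too good. Coverage of the nominal 95% interval is then about 93% down to 80% for an SD of 25 to 30 mm. The gap and SD are assumptions, because the documents give neither; if loss is unrelated to outcome, the bias is zero. A reader might infer that the trial's conclusion is at risk. It is not: the composite test is handled separately.

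**What to change.** Add to section 3.2.7, for low back VAS, leg VAS and ODI:

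1. Keep the observed-case table and show the number observed at each visit.
2. Report mean change from baseline with a 95% interval from a likelihood-based repeated-measures model, with visit as a factor and unstructured covariance. Include baseline as a response, so that treated subjects with no post-baseline score still contribute and the population matches section 3.2.3. Such a model imputes nothing, so the no-imputation sentence can stay.
3. Add a simple missing-not-at-random sensitivity analysis, such as shifting the expected 24-month score of lost subjects by a stated delta (for instance 10 and 20 mm on VAS) and reporting the resulting mean.

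Cost: a paragraph of text and a little analysis work, with no new data, visits or subjects. The downside is reliance on missing at random in item 2, which item 3 is there to probe.
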